11.10. Study Completion

The study will conclude after the earliest of one of following occurrences: (1) one arm is determined to be superior at one of the three interim analyses (per Section 12.3.1), or (2) a sufficient number of shock episodes have occurred to provide the desired power. It is expected that the last enrolled patient will be followed for approximately 18 months and the first enrolled patient will be followed for approximately 60 months. Sites will continue to follow subjects until notified of follow-up completion. Sites will be notified when subject follow-up is complete for the study.

11.11. Source Documents

Original source documents are required to be retained at the center. Where copies of the original source document as well as printouts of original electronic source documents are

retained, these shall be signed and dated by a member of the investigational site team with a statement that it is a true reproduction of the original source document.

NOTE: If thermal paper from the device programmer was used for source documentation, photocopies or printed pdfs should be prepared and kept for source documentation.

12. Statistical Considerations

12.1. Endpoints

12.1.1. Primary Endpoint - Time-to-First All-Cause Shock

The incidence of all-cause shocks in subjects programmed with shocks only will be compared with subjects programmed to standard therapy (ATP and shock) to assess equivalency.

12.1.1.1. Hypotheses

The hazard ratio of all-cause shocks will be used to evaluate the equivalence of shocks only programming and standard therapy. A relative equivalence margin of 35% in each direction will be employed. The following hypotheses will be used.

H₀: Hazard Ratio ≤ 0.65 or Hazard Ratio $\geq (1/0.65)$

 H_A : 0.65 < Hazard Ratio < (1/0.65)

12.1.1.2. Sample Size

A total of 2600 subjects – 1300 per group – will be required to sufficiently power the primary endpoint. The sample size of 2600 subjects will provide the number of primary endpoint events necessary to power the Primary Endpoint. Two assumption scenarios were considered to determine the required sample size.

	Scenario 1	Scenario 2
Expected all-cause shock rate in each group	6%	7%
Alpha	5%	5%
Power	90%	90%
Equivalence Margin	(0.65 - [1/0.65]) = (0.65 - 1.54)	(0.65 - [1/0.65]) = (0.65 - 1.54)
Attrition at 18 months	10%	10%
Enrollment Period	42 months	42 months
Follow-up Period	First Patient: 60 months	First Patient: 54 months
Tonow-up Terrou	Final Patient: 18 months	Final Patient: 12 months
Maximum Trial Duration	60 months	54 months

12.1.1.3. Statistical Methods

All implanted and randomized subjects will contribute to the analysis of the Primary Endpoint. Cox proportional hazards modeling will be performed, with time-to-first shock therapy episode used as the outcome and programming scheme used as the covariate in the model. Traditional therapy will be considered the reference group in the analysis. Each subject's first shock therapy episode will contribute to the analysis. Subjects without a shock therapy episode will be censored at their date of death, withdrawal, study exit or on the date of the data snapshot, whichever occurs first. From the Cox model, the hazard ratio and corresponding confidence interval for programming scheme will be calculated. If the confidence interval for the hazard ratio is fully contained within the equivalence region – between 0.65 and 1.54 – equivalence of shocks only and standard programming will be concluded.

If equivalency cannot be established, further testing for superiority will be performed without need for a multiplicity adjustment to the significance level of the test beyond the adjustment necessary to accommodate the interim superiority tests. This additional testing is possible because the equivalence test is comprised of two separate one-sided non-inferiority tests. If non-inferiority is established for only one of the two one-sided non-inferiority tests, superiority can further be tested, per gating methodology.

The following table outlines the possible results and conclusions that can be drawn from the Primary Endpoint analysis.

Result of Lower Confidence Limit of Confidence Interval	Result of Upper Confidence Limit of Confidence Interval	Conclusion
>0.65	<1.54	Equivalence of shocks only to standard therapy
≤0.65	≥1 and <1.54	Non-inferiority of shocks only to standard therapy
<0.65	<1	Superiority of shocks only to standard therapy
≤1 and >0.65	>1.54	Non-inferiority of standard therapy to shocks only
>1	>1.54	Superiority of standard therapy to shocks only

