8.2. Treatment Assignment

Any patient meeting all inclusion and no exclusion criteria is enrollment eligible for the APPRAISE ATP study. Patients are considered enrolled in the study once the informed consent form (ICF) has been executed.

Randomization schemes can be obtained by logging onto the electronic data capture system (EDC) and registering the patient. Randomization will be in a 1:1 ratio of either treatment arm and will be stratified by ischemic etiology, history of atrial fibrillation, and diabetes.

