11.4. Randomization Assignment

Randomization by the EDC system and device programming to randomized treatment arm can be performed at the enrollment visit once the patient has completed the informed consent process. Randomization will be obtained through the EDC system. Subject data regarding ischemic etiology, history of atrial fibrillation and diabetes must be entered in the EDC database as randomization cannot occur without these three data points.

If randomization and subsequent device programming to randomized arm is not performed at the enrollment visit, the randomization and device programming visit must occur on the same day, and cannot exceed 60 calendar days post implant. Prior to randomization, sites need to verify that subjects still meet inclusion criteria and no exclusion criteria.

Every reasonable attempt will be made to have subjects blinded to their randomized treatment arm assignment throughout the trial.

Table 11.4-1: Source Document Requirements – Randomization

Data Collection Requirement	Retention of Original Source Documentation
Subject randomization assignment	Investigational Center
• Reportable AE's, if applicable	

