12.1.2.2. Statistical Methods

All implanted and randomized subjects will contribute to the analysis of Secondary Endpoint 1. Cox proportional hazards modeling will be performed, with time-to-first shock therapy episode or death used as the outcome and programming scheme used as the covariate in the model. Traditional therapy will be considered the reference group in the analysis. Each subject's death or first shock therapy episode will contribute to the analysis. Subjects that survived the follow-up duration without a shock therapy episode will be censored at their date of withdrawal, study exit or on the date of the data snapshot, whichever occurs first. From the Cox model, the hazard ratio and corresponding confidence interval for programming scheme will be calculated. If the confidence interval for the hazard ratio is fully contained within the equivalence region – between 0.65 and 1.54 – equivalence of shocks only and standard programming will be concluded. In the event that equivalency cannot be established, superiority testing will be performed, employing similar methodology to that described for the Primary Endpoint.

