12.1.3.2. Statistical Methods

All implanted and randomized subjects will contribute to the analysis of Secondary Endpoint 2. Cox proportional hazards modeling will be performed, with time-to- death used as the outcome and programming scheme used as the covariate in the model. Traditional therapy will be considered the reference group in the analysis. Each subject's death will contribute to the analysis. Subjects that survived the follow-up duration will be censored at their date of withdrawal, study exit or on the date of the data snapshot, whichever occurs first. From the Cox model, the hazard ratio and corresponding confidence interval for programming scheme will be calculated. If the confidence interval for the hazard ratio is fully contained within the equivalence region – between 0.65 and 1.54 – equivalence of shocks only and standard programming will be concluded. In the event that equivalency cannot be established, superiority testing will be performed, employing similar methodology to that described for the Primary Endpoint.

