12.1.4.2. Statistical Methods

All implanted and randomized subjects will contribute to the analysis of Secondary Endpoint 3. Cox proportional hazards modeling will be performed, with time-to-first appropriate shock therapy episode used as the outcome and programming scheme used as the covariate in the model. Traditional therapy will be considered the reference group in the analysis. Each subject's first appropriate shock therapy episode will contribute to the analysis. Subjects without an appropriate shock therapy episode will be censored at their date of death, withdrawal, study exit or on the date of the data snapshot, whichever occurs first. From the Cox model, the hazard ratio and corresponding confidence interval for programming scheme will be calculated. If the confidence interval for the hazard ratio is fully contained within the equivalence region – between 0.65 and 1.54 – equivalence of shocks only and standard programming will be concluded. In the event that equivalency cannot be established, superiority testing will be performed, employing similar methodology to that described for the Primary Endpoint.

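### Randomization is stratified by three baseline factors, but the primary and all four secondary Cox models fit programming arm alone

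*Combined protocol and SAP*

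**What the plan says.** Section 8.2 says that 1:1 randomization "will be stratified by ischemic etiology, history of atrial fibrillation, and diabetes". Section 11.4 makes the three values compulsory in the EDC, since "randomization cannot occur without these three data points", so they are complete by design for every randomized subject.

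Section 12.1.1.1 defines the comparison: "The hazard ratio of all-cause shocks will be used to evaluate the equivalence of shocks only programming and standard therapy", with margins of 0.65 and 1/0.65. Section 12.1.1.3 specifies Cox regression "with time-to-first shock therapy episode used as the outcome and programming scheme used as the covariate in the model". The secondary endpoints follow the same pattern:

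- shock or death (12.1.2.2): "with time-to-first shock therapy episode or death used as the outcome and programming scheme used as the covariate in the model";
- death (12.1.3.2): "with time-to- death used as the outcome and programming scheme used as the covariate in the model";
- appropriate shock (12.1.4.2): "with time-to-first appropriate shock therapy episode used as the outcome and programming scheme used as the covariate in the model";
- inappropriate shock (12.1.5.2): the same construction, with arm as the only term.

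No other section supplies a stratum-adjusted arm effect. Section 12.2.1 defines analysis sets, and 12.3.1 gives alpha levels for the interim superiority looks without naming a model. Section 12.3.2 covers interactions and subgroups, 12.1.6.1 models other outcomes, and 12.3.3 adds geography to assess poolability.

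**The concern.** An analysis would normally reflect the factors used to stratify the allocation. If those factors predict shocks, leaving them out has two consequences.

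- **Standard error.** Stratified allocation balances the factors between arms, so the arm-only log hazard ratio varies less from trial to trial than its model standard error says. The superiority tests then run below their nominal level and lose power. This does not depend on how the margin is read, because the marginal and conditional hazard ratios coincide at 1. These tests have consequences: under Section 11.10 the study ends early if "one arm is determined to be superior at one of the three interim analyses", and superiority is also the gated fallback when equivalence fails (12.1.1.3).
- **Estimand.** Away from 1, the arm-only hazard ratio is closer to 1 than the within-stratum hazard ratio. In an equivalence trial that is the lenient direction. It matters only if the margin is meant conditionally, and Section 12.1.1.1 does not say.

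**Working it through.** **Inputs from the plan.** N = 2600, 1:1; shock rate 6% (Scenario 1) or 7% (Scenario 2); 10% attrition at 18 months; 42 months' enrollment; follow-up 18–60 or 12–54 months; power 90% (12.1.1.2). Final-look level 0.022 (12.3.1), taken as one-sided because 12.2.2 allots 2.5% to each direction.

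**Assumptions.** The table in 12.1.1.2 gives no time base for the shock rates; they are read at 18 months. Section 12.1.1.3 gives no confidence level; 95% is used. The documents give no prevalences or effects for the factors; prevalences of 50/30/35% and a common factor HR of 1.3, 1.5, 2 or 3 are assumed, with permuted blocks of 4 in the eight strata.

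**Step 1: the plan's sample size.** Events needed for two one-sided tests at true HR 1:

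d = 4(z₁₋ₐ + z₀.₉₅)² / (ln 0.65)²

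- a = 0.025: 4(1.960 + 1.645)² / 0.1856 ≈ 280.
- a = 0.022: 4(2.014 + 1.645)² / 0.1856 ≈ 289.

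Expected events in Scenario 1, with exponential hazards: λ = −ln(0.94)/1.5 = 0.0413 and μ = −ln(0.90)/1.5 = 0.0702 per year, and censoring uniform on 1.5 to 5 years. The event probability is 0.370 × (1 − 0.700) ≈ 0.111, or about 288 events in 2600. Scenario 2 gives 290. At a = 0.022 the required N is 2604 and 2590, so the planned 2600 at 90% power reproduces. At a = 0.025 power is 91.0% and 91.2%. Reading the rates per year instead gives 418 and 420 events and about 98.5% power at a = 0.025, which does not match the plan.

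**Step 2: what the arm-only model estimates.** Its large-sample limit b solves the expected score equation

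∫ [e₁(t) − (e₀(t) + e₁(t)) · r₁(t)eᵇ / (r₀(t) + r₁(t)eᵇ)] dt = 0,

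where rₐ and eₐ are the expected numbers at risk and event intensities in arm a, summed over the eight strata. The two scenarios agree to about 0.001 in HR.

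**Step 3: operating characteristics.** 20,000 simulated trials per setting, Scenario 1, each analysed by arm-only Cox and by Cox with arm plus three binary covariates (adjusted).

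| Factor HR | 1.3 | 1.5 | 2 | 3 |
|---|---|---|---|---|
| Events at HR 1 | 288 | 287 | 284 | 278 |
| Arm-only limit, conditional HR 1.538 | 1.536 | 1.532 | 1.518 | 1.486 |
| Arm-only limit, conditional HR 0.65 | 0.651 | 0.652 | 0.656 | 0.666 |
| Arm-only model SE / true SD at HR 1 | 0.1183 / 0.1181 | 0.1184 / 0.1174 | 0.1189 / 0.1157 | 0.1204 / 0.1143 |
| Adjusted model SE / true SD at HR 1 | 0.1183 / 0.1185 | 0.1184 / 0.1184 | 0.1190 / 0.1182 | 0.1204 / 0.1209 |
| Superiority rejection at HR 1, level 2.2%: arm-only / adjusted | 2.24 / 2.25% | 2.23 / 2.34% | 1.87 / 2.07% | 1.52 / 2.10% |
| Superiority power, conditional HR 0.70, one look at 0.022: arm-only | 77.5% | 77.1% | 75.9% | 72.6% |
| Gain from adjustment, points | 0.2 | 0.6 | 1.5 | 4.1 |
| False equivalence, conditional margin: arm-only / adjusted | 2.7 / 2.6% | 2.9 / 2.7% | 3.1 / 2.7% | 4.1 / 2.5% |
| False equivalence, marginal margin: arm-only | 2.6% | 2.3% | 2.3% | 1.8% |
| Equivalence concluded at HR 1: arm-only / adjusted | 90.52 / 90.32% | 90.53 / 90.27% | 90.98 / 90.15% | 90.71 / 88.80% |

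The Monte Carlo SE of a single rate near 2.5% is about 0.11 point. Paired differences are tighter: at factor HR 2, the power gain is 1.47 (SE 0.11) and the loss of equivalence at HR 1 is 0.83 (SE 0.10).

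**Step 4: cross-checks.** The standard errors roughly explain the rejection rates. At factor HR 2, 0.1189/0.1157 = 1.028, and 2.014 × 1.028 = 2.070 corresponds to 1.9%. At factor HR 3, 0.1204/0.1143 = 1.053, and 2.014 × 1.053 = 2.121 corresponds to 1.7%. The simulated rates are 1.87% and 1.52%.

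A second simulation (prevalences 55/25/35%, 3,000 trials) gave arm-only against adjusted false equivalence of 2.6 / 2.5%, 2.8 / 2.7% and 3.5 / 2.6% for factor HRs of (1.2, 1.5, 1.2), (1.5, 2, 1.5) and (2, 3, 2). A third (4,000 trials, eight-stratum Cox, factor HR 2) gave arm-only against stratified false equivalence of 3.2 / 2.6% and superiority power of 75.1 / 76.6%.

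**The case against.** The arm-only analysis is valid. Section 12.1.1.3 compares the confidence interval from that model with 0.65 to 1.54, so in operation the margin applies to the arm-only hazard ratio. On that reading false equivalence is nominal to conservative. The 3.1% needs a conditional margin that the plan nowhere states. Adjustment also lowers the chance of concluding equivalence at HR 1, which is the primary aim. A visible effect needs all three factors at HR 2 together, an eightfold hazard range across strata (2³), and nothing in the documents supports that. The plan already names one model for each endpoint in advance.

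Much of this stands. If the margin is marginal, the case rests on the superiority tests alone. The loss in equivalence is real, and the adjusted model should not be presented as a power gain for the primary test. The calculations also have limits. Superiority was computed at a single look, not with the interim boundaries. No secondary endpoint was simulated. The simulated trials had constant factor effects without interactions, which is the adjusted model's own form.

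It does not remove the point. The loss of efficiency in the superiority tests arises on either reading of the margin. The same mechanism applies to the interim looks and to any secondary endpoint that the factors predict. The plan also offers no analysis by the strata it randomizes within, not even as a sensitivity analysis.

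**Conclusion.** The point holds as a modest, inexpensive improvement. No planning figure breaks. For factor HRs up to 1.5 the omission is negligible. With all three factors at HR 2, the arm-only superiority test rejects 1.9% of the time at a nominal 2.2%. It also gives up about 1.5 points of power at HR 0.70. At factor HR 3 the power loss is about 4 points. False equivalence exceeds 2.5% materially only if the margin is conditional: 3.1% at factor HR 2 and 4.1% at factor HR 3.

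These sizes rest on the assumed prevalences and factor effects, the 18-month reading of the 6% rate, and a 95% interval. The mismatch between Sections 8.2 and 12.1 rests on none of them.

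**What to change.** In 12.1.1.3, 12.1.2.2, 12.1.3.2, 12.1.4.2 and 12.1.5.2, and for the interim looks in 12.3.1, prespecify one model: Cox regression with programming scheme plus ischemic etiology, history of atrial fibrillation and diabetes as three binary covariates, using the values entered in the EDC for randomization. State that the 0.65 to 1.54 margin and the superiority tests refer to the programming-scheme hazard ratio from this model. Keep the arm-only model as a sensitivity analysis. A Cox model stratified by the eight cells performs almost identically (loss of equivalence at HR 1 of 0.2 / 0.3 / 0.9 / 2.0 points for factor HRs 1.3 / 1.5 / 2 / 3), so either will do if it is named in advance.

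The cost is one sentence per endpoint section, one in 12.3.1 and one on the margin, through the amended-SAP route in 12.3.4 before the blind is broken. No data, visits or patients are added, and N stays at 2600. The price is a lower chance of concluding equivalence at HR 1: 0.2 to 0.8 point for factor HRs 1.3 to 2 (still at least 90.1%) and 1.9 points at factor HR 3 (88.8%, below the planned 90%). Stronger factors could cost more.

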12.1.2. Secondary Endpoint 1 - Time-to-First All-Cause Shock or Death from Any Cause

The incidence of all-cause shocks or death in subjects programmed with shocks only will be compared with subjects programmed to standard therapy (ATP and shock) to assess equivalency.

12.1.2.1. Hypotheses

The hazard ratio of all-cause shocks or death will be used to evaluate the equivalence of shocks only programming and standard therapy. A relative equivalence margin of 35% in each direction will be employed. The following hypotheses will be used.

H0: Hazard Ratio ≤ 0.65 or Hazard Ratio $\geq (1/0.65)$

HA: 0.65 < Hazard Ratio < (1/0.65)

12.1.2.2. Statistical Methods

All implanted and randomized subjects will contribute to the analysis of Secondary Endpoint 1. Cox proportional hazards modeling will be performed, with time-to-first shock therapy episode or death used as the outcome and programming scheme used as the covariate in the model. Traditional therapy will be considered the reference group in the analysis. Each subject's death or first shock therapy episode will contribute to the analysis. Subjects that survived the follow-up duration without a shock therapy episode will be censored at their date of withdrawal, study exit or on the date of the data snapshot, whichever occurs first. From the Cox model, the hazard ratio and corresponding confidence interval for programming scheme will be calculated. If the confidence interval for the hazard ratio is fully contained within the equivalence region – between 0.65 and 1.54 – equivalence of shocks only and standard programming will be concluded. In the event that equivalency cannot be established, superiority testing will be performed, employing similar methodology to that described for the Primary Endpoint.

12.1.3. Secondary Endpoint 2 – Time-to-Death from Any Cause

Hazard of death from any cause in subjects programmed with shocks only will be compared with subjects programmed to standard therapy (ATP and shock) to assess equivalency.

12.1.3.1. Hypotheses

The hazard ratio of death will be used to evaluate the equivalence of shocks only programming and standard therapy. A relative equivalence margin of 35% in each direction will be employed. The following hypotheses will be used.

 H_0 : Hazard Ratio ≤ 0.65 or Hazard Ratio $\geq (1/0.65)$

 H_A : 0.65 < Hazard Ratio < (1/0.65)

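### The 0.65–1.54 margin set for shocks is reused without justification for death and for shock-or-death, so a material mortality excess could be labelled equivalent

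*Combined protocol and SAP*

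**What the plan says.** Section 12.1.1.1 sets the margin for all-cause shock, and Section 12.1.1.2 ties the sample size to that endpoint: "A total of 2600 subjects – 1300 per group – will be required to sufficiently power the primary endpoint".

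Section 12.1.3.1 carries the margin over to all-cause death: "The hazard ratio of death will be used to evaluate the equivalence of shocks only programming and standard therapy", and "A relative equivalence margin of 35% in each direction will be employed". Section 12.1.3.2 orders a conclusion of equivalence when the confidence interval is "fully contained within the equivalence region – between 0.65 and 1.54". It then adds: "In the event that equivalency cannot be established, superiority testing will be performed".

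Sections 12.1.2.1 and 12.1.2.2 do the same for the composite: "The hazard ratio of all-cause shocks or death will be used to evaluate the equivalence of shocks only programming and standard therapy".

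No section explains why 1.54 is tolerable for mortality. None gives an expected death rate or the power for a secondary endpoint, and none states the confidence level of the interval. The only related input is the 10% in the row "Attrition at 18 months" of the sample-size table, which does not say how much of it is death. Section 10.2 lists death among the withdrawal reasons.

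**The concern.** A margin that may be acceptable for a device shock is not automatically acceptable for death, and the plan does not argue that it is. The Introduction cites an association between inappropriate ATP and mortality as a reason for further study, so the death result will be read as evidence in its own right.

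The rule also has no step that flags harm. Superiority is tested only after equivalence fails, so an interval lying entirely between 1 and 1.54 ends as equivalence.

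For shock-or-death the same margin is looser than it looks. If deaths are similar in both arms, they pull the composite hazard ratio towards 1.

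**Working it through.** **Inputs.** From Section 12.1.1.2, Scenario 1: 2600 subjects at 1:1, 42 months of enrolment, follow-up of 18 to 60 months, 6% shock rate, 10% attrition at 18 months, 90% power. The margin is |ln HR| < −ln 0.65 = 0.4308.

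**Assumptions.** The 6% is an 18-month rate (the table gives no time base). Times are exponential and accrual is uniform. SE(ln HR) = 2/√events. The interval is 95%. Deaths are part of attrition, with the share varied.

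**Reproducing the plan's own figure.**
- Shock hazard λ = −ln(0.94)/1.5 = 0.0413 per year. Attrition hazard α = −ln(0.90)/1.5 = 0.0702 per year.
- Expected events of a type with hazard h, when the total exit hazard is k: 2600 × (h/k) × the mean of (1 − e^(−ku)) for u uniform on 1.5 to 5 years.
- First shocks (h = λ, k = λ + α): 288.
- Events needed at the final one-sided level of 0.022 in Section 12.3.1: 4(2.014 + 1.645)²/0.4308² = 289.

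So 2600 is reproduced, and the model is a fair reading of the design.

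**Death.** Put h = share × α and k = α.
- Largest observed HR that passes: exp(0.4308 − z × 2/√d).
- Chance of the label at true HR θ: Φ((0.4308 − z·SE − ln θ)/SE) − Φ((−0.4308 + z·SE − ln θ)/SE).

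For 263 deaths: SE = 0.1234, and 0.4308 − 1.96 × 0.1234 = 0.189, which gives an HR of 1.21.

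| Deaths as share of attrition | Deaths | Largest passing HR, 95% CI | Largest passing HR, 90% CI | Chance of label if true HR = 1.25, 95% CI |
|---|---|---|---|---|
| 25% | 131 | 1.09 | 1.15 | 18% |
| 50% | 263 | 1.21 | 1.26 | 39% |
| 75% | 394 | 1.26 | 1.30 | 54% |
| 100% (limiting case) | 525 | 1.30 | 1.33 | 66% |

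With a 95.6% interval, which matches the 0.022 level, the limits are 1.08, 1.20, 1.26 and 1.29.

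Deaths needed with a 95% interval before an observed HR of 1.20 or 1.30 can pass: (2 × 1.96/(0.4308 − ln HR))² = 249 and 542.

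**Interval wholly above 1 yet inside the margin.** This needs 2 × 1.96 × 2/√d < 0.4308, so d > 331.2, or about 332 deaths (234 with a 90% interval).

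**Composite.** Let the true shock HR be 1/0.65 and the death HR be 1, with death hazard m = share × α. The composite HR is (λ/0.65 + m)/(λ + m). Events are averaged over the two arms.

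| Share | Composite HR | Events | Chance composite is called equivalent, 95% CI |
|---|---|---|---|
| 25% | 1.38 | 478 | 23% |
| 50% | 1.29 | 599 | 57% |
| 75% | 1.24 | 719 | 83% |
| 100% | 1.20 | 840 | 95% |

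At that shock HR the primary endpoint meets its own rule at most 2.5% of the time.

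**The case against.** The strongest reply is that the size rests on a death count the plan does not give. That stands. At 131 deaths the largest passing observed HR is 1.09, and the label is earned only 39% of the time even if the true HR is 1. At 53 deaths (a 10% share) it could never be earned. The 100% share is a limiting case, because Section 10.2 lists many withdrawals other than death and Section 9.3 excludes several high-risk groups.

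A reader might infer that the plan accepts a 54% higher death hazard as equivalent. It does not. The whole interval must lie inside the margin, so a true HR of 1.54 passes at most 2.5% of the time with a 95% interval. A reader might also infer that a 20–30% excess is bound to be labelled equivalent. That requires roughly 250 to 540 deaths, and the documents do not establish such a count.

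On the composite, the primary result is reported alongside it, and no text lets the composite override a failed primary. Combining death with shock also has a legitimate purpose, because the primary analysis censors at death. This makes the composite the lesser point.

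It is also true that the HR and its interval will be calculated, that an independent monitoring committee reviews safety (Section 21.1), and that equivalence is the trial's stated objective. None of these supplies a reason for 1.54 on mortality or changes the conclusion that Section 12.1.3.2 prescribes.

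**Conclusion.** The point holds as an unjustified reuse of a margin, joined to a rule that can give a misleading label. Under the assumptions above, an observed death excess of 9 to 30% could be called equivalent with a 95% interval, depending on the death count. A true 25% excess would be so labelled 18 to 66% of the time. From about 332 deaths the label could even sit on a statistically significant excess.

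The composite could be called equivalent 23 to 95% of the time with shocks at the margin and no effect on death, although the primary would then fail at least 97.5% of the time.

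The copied margin, the absence of a justification and the order of testing are in the text. The death share and the confidence level are assumptions. The risk lies in how secondary endpoints are labelled; the primary analysis is unaffected.

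**What to change.** In Section 12.1.3, remove the rule that concludes equivalence for death. Report the hazard ratio with its 95% CI and a two-sided test of difference, not conditional on any equivalence result. Alternatively, pre-specify a separately justified death-specific upper limit before the first interim analysis, with the confidence level and expected death count stated. A tight limit may be out of reach: as an illustration, a two-sided margin of 1.25 would need 4(1.96 + 1.645)²/(ln 1.25)² ≈ 1,044 deaths for 90% power, against 525 in the limiting case.

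In Section 12.1.2, either do the same or state that the composite cannot support equivalence on shocks when the primary endpoint fails.

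The change is to wording only. It costs the sponsor an equivalence label on secondary endpoints and needs no extra data or patients.
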